## **2. Subject Selection**

**Inclusion Criteria:** The study involves males and females aged  $\geq 21$  years who are English and Spanish-speaking patients at a Piedmont Health Services primary care health center; and with a BMI between 25-40 kg/m^2 and weight less than 380 pounds. Eligible participants will have had a non-urgent visit to a Piedmont Health clinic within the last 2 weeks. Eligible participants will also have a cell phone and be willing to receive study-related text messages (3-12 messages per week).

**Exclusion Criteria:** Potential participants cannot: be a current Piedmont Health employee; currently or recently (within the past six months) pregnant or planning on becoming pregnant in the next 12 months; be currently or recently (past 2 months) lactating; have prior or planned bariatric surgery; have a diagnosis contraindicating weight loss (e.g., active malignancy); have a history of a cardiovascular event (stroke, MI); or have been hospitalized for a mental health issue in the last 12 months; have a diagnosis of end-stage kidney disease (ESRD) in the medical record; or due to investigator discretion for a potential health or safety issue. Potential participants who have a history of a coronary artery revascularization (in last 12 months) will be allowed to participate in the study with provider approval (See Appendix C).

**Sample size:** We will recruit up to 455 adult men and women, who speak either English or Spanish. At least 30% of the sample will be male (we recently recruited a 31% male sample in Track). The sample size calculation is based on the primary aim examining differences in the time to gain  $\geq 3\%$  of baseline weight between intervention and control groups. Based on Shape's clinical data, we assume a 5% sample loss for each group per month of the study. A sample of N=192 per group (Total N=384) allows us to test the difference between the two distributions with greater than 80% power. Factoring in an additional expected sample loss of 15% (those with no clinical data past baseline) gives a final sample size of N=221 per group (Total N=442, with the possibility of enrolling up to 455).

For the qualitative Balance implementation sub-study, we will recruit up to 25 Piedmont Health employees in varying roles and across the participating sites and leadership team.

For the Balance pragmatic design survey, we will invite via email up to 25 current or former Balance research team members at Duke and Piedmont Health Services staff (including leadership and dietitians) to complete the voluntary online Qualtrics survey (See Appendix R for the recruitment email template).

**Recruitment:** To enhance the pragmatic design, study recruitment will occur via two methods: 1) provider referral and 2) mailed materials to potentially-eligible patients based on lists run by Piedmont Health (See Appendices J-L).

1) Recruitment via Provider Referral: This approach was suggested and preferred by the Piedmont Health medical director and associate medical director/medical informatics director and is a current practice at Piedmont Health. Recruitment will occur as follows:

During regular outpatient appointments, Piedmont Health providers will introduce Balance to their patients and gauge their interest in being contacted by Duke research staff to learn more about the study (See Appendix E). Patients who express interest in Balance will be informed that a HIPAA authorization form needs to be signed to allow Duke research staff to access their information and contact them for follow-up. The provider will then give patients a brochure and HIPAA authorization form, written in Spanish or English. The study brochure and HIPAA authorization form will be reviewed with patients by a Piedmont staff member and signed copies returned via the following methods: placed in a lockbox in the clinic; securely scanned by the Piedmont Health provider or staff member and uploaded to a restricted Duke Box folder set up in a Duke-provisioned Box account; or emailed the Balance study Duke email address or the Duke email address of authorized study personnel, such as the lead research assistant or study coordinator. The forms may also be returned in-person to a Duke research assistant, if in the clinic at time of referral. (See Appendix I for research assistant script). A copy of the IRB-approved verbal consent document will also be reviewed and given to patients to review and take home, if interested. Any questions about the study will also be addressed. Duke research assistants will then confirm eligibility of patients who have signed the HIPAA authorization form by reviewing their electronic medical record and create a new participant record in the Duke REDCap Balance project with the details from the HIPAA form (e.g. name, DOB, contact phone numbers, signature date, HIPAA form recruitment method, primary health center, etc.) into the REDCap project for the study. At the same time, s/he will also enter the patient ID number from the medical record into REDCap. This is to ensure duplicate records for the same participant are not created within our study database during the estimated two-year recruitment timeline. Because of how the REDCap project was created for the purposes of Balance, matching new patients with patients who are already in the database by the unique identifier of patient ID at time of data entry will be the only way to prevent duplicate records for the same person (i.e. when people go back for appointments in the future during our active recruitment period and could be accidentally re-recruited in the health center).

If eligible based on chart review, the Duke research assistant will then contact the patient via phone or in-person at the clinic. The patient will be screened, and if interested and still eligible to participate, will be verbally consented and enrolled, on the phone or in-person, by the research assistant. Trainings regarding the study purpose, directions about participant eligibility, intervention components, and processes to refer to the study will be conducted at participating Piedmont Health sites with involved staff.

2) Recruitment via Mail: To enhance our recruitment success and expand recruitment to other, more rural Piedmont Health clinic locations, we plan to reach out to potentially-eligible patients via mail in advance of their medical appointments. (Please also see Appendix J for the partial HIPAA authorization waiver). This will occur as follows:

Once or twice per month, Piedmont Health staff will run a report of all patients who are  $\geq 21$  years old; not currently pregnant; do not have end-stage renal disease, have a last recorded BMI and weight within our target range; speak English or Spanish as their primary language; and who have an upcoming medical appointment within the next 4-6 weeks at one of the participating Piedmont Health community health centers. The Piedmont report will be exported as a spreadsheet and securely sent (via their encrypted email system that they use to send sensitive emails/email that contains ePHI or via a restricted folder in within the Balance Duke Box folder) to the Balance study coordinator with the following information: patient name; gender (for letter salutation purposes); Date of Birth; mailing address; telephone number(s); email address; preferred language (Spanish/English); primary community health center; and upcoming appointment date. From this list, we would send a cover letter (See Appendix K); Balance study information (See Appendix F); and two copies of the HIPAA authorization form (See Appendix D) via postal mail. We would request that interested patients sign and return one copy of the form to us via mail to our office or printed, signed, scanned and returned as an attachment via email to our Duke Balance

email address. The patient would also have the option of returning the form to us during or immediately after their medical appointment at the clinic. The other copy of the HIPAA form would be for the patient to keep for his/her records.

In the cover letter, we would explain the study and the waiting period of 10 days before we would contact the patient for follow-up. During those first 10 days, if patients contact us via mail, phone or email and state they wish to be removed from our list, we will document their lack of interest in the study and not contact the participant further.

If after 10 days, the participant has not opted out of contact, a Duke research assistant or Piedmont provider will contact the participant via phone or email (See Appendix L). We will contact participants no more than twice per week via phone and/or email before their appointment and no more than twice a week following their scheduled appointment time. The reason for contacting participants after the appointment time is that participants remain eligible up to 14 days after their appointment. If we do not receive a signed form within 14 days after the appointment date, we will not follow up with them again via mail at that timepoint. If the participant expresses disinterest within 14 days post-appointment, we will document this in our database and no future follow-up contact would occur.

During the recruitment phase of the study, it is necessary to keep participant names, dates of birth and contact information to cross-check previous recruitment and enrollment lists. These lists will be stored in Duke Box or within our Balance REDCap project. We will keep these lists for our recruitment period to ensure we do not inadvertently contact the same patient multiple times; contact participants who have told us they do not wish to be contacted; or contact participants who have already been screened, consented and/or enrolled at another time point. Once the recruitment phase is over and we have enrolled all participants in Balance, we will redact the PHI from these recruitment lists.

If we receive a signed HIPAA authorization form from this recruitment method, we will complete the same study procedures as for the provider referral method, i.e. a brief chart screen, phone screen, verbal consent, and phone enrollment, as described previously and below.

For both recruitment methods, we will screen participants, consent those to Balance who meet eligibility criteria over the phone or in-person in the clinic, and conduct survey and randomization activities as outlined above in the Data Collection section: Baseline Assessment. Study surveys will eliminate or define medical terms and use simple sentence structure and vocabulary. As in previous trials we will offer all recruitment, enrollment, and assessment activities in both English and Spanish in order to maximize the representativeness of the study sample. For both recruitment methods, we will reach out to potential participants via phone call, text message and/or email to assess interest in the study, and if interested, for phone screening, consent and enrollment.

We will randomize participants in permuted blocks, stratified by health center to balance assignment by community health center. With our design, research staff and participants cannot reasonably be blinded to allocation. However, to reduce the potential for biased outcomes, we take steps to segregate research staff from those involved in intervention design and evaluation. Our work demonstrates the feasibility of this methodology; indeed, we designed this strategy together with Piedmont and they agree that it will be minimally burdensome to clinic operations.

Patients who sign the HIPAA authorization form but are ineligible for the study based on screen will be informed they are not eligible for Balance. If the only reason a participant is ineligible for the study is too high based on BMI/weight from their chart (i.e. BMI was above 40 kg/m^2; and/or weight was greater than 380 lbs), s/he will be mailed a cover letter; copy of health education materials based on the NHLBI's "Aim for a Healthy Weight" booklet; and a printed copy of an IRB-approved Charge study recruitment

flyer (Duke Campus IRB Protocol Number D0752) with information about how to sign up for that trial, if interested (for English-speakers only), during the time that Charge is actively recruiting. (See Appendix C for eligibility screen).

To recruit up to 25 Piedmont Health providers and staff for the qualitative sub-study, we will first reach out to individual stakeholders who were involved in the implementation of the project via email and assess their interest in possibly participating. If the employee declines possibly participating, we will not follow up further. If s/he expresses interest, we will coordinate a date and time to conduct the verbal consent process (See Appendix P) and semi-structured interview (See Appendix Q), either in-person or on the phone.

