# **STUDY PROTOCOL**

## 1. Research Design

**Overall study aim:** This will be a pragmatic, patient-randomized controlled effectiveness trial. We will randomize up to 455 overweight and obese adult participants to a 12-month weight gain prevention intervention (Balance, or *Equilibrio* in Spanish) or to usual care. Our primary outcome will be weight gain prevention over 24 months, defined as  $\leq 3\%$  change in initial body weight over 24 months. We will gather all follow-up patient data to assess outcomes from their Piedmont electronic health record. We will not have any intervention contact with participants during the final 12 months, with the exception of a Balance intervention satisfaction survey. Funding for this trial was provided by the National Institutes of Health, National Institute of Diabetes and Digestive and Kidney Diseases on May 13, 2016. Funding continued through April 30, 2023.

**Background:** Up to 50% of obese patients are not interested in, or ready for, weight loss. Clinical practice guidelines clearly recommend that these patients avoid gaining weight. Doing so might contain, or even attenuate, the adverse cardiometabolic risks that accrue with additional weight gain. However, despite this clinical guideline, weight gain prevention interventions are not available in primary care practice. This evidence gap disproportionately affects medically vulnerable patients -- those who are low-income, often racial/ethnic minority, and may reside in rural settings. These patients have the highest rates of obesity and weight gain, but the least interest in, readiness for, and success with weight loss. The implications for these patients are clear: without intervention, most will continue to gain weight and incur cardiometabolic risks. For obese medically vulnerable patients, weight gain prevention is a priority but treatment options do not exist.

**Pragmatic Effectiveness Trial:** This will be a pragmatic effectiveness trial to test the Balance intervention in rural community health centers. We will randomize up to 455 overweight and obese adults to either: 1) usual care, or 2) a 12-month weight gain prevention intervention, including mHealth self-monitoring and feedback, skills training videos, and responsive coaching from a clinic dietitian. Our primary outcome is weight gain prevention at 24 months.

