At Piedmont, weight and blood pressure are measured at all visits, including for acute care. Our proposed lab tests are also commonly administered. We will closely monitor patients' medical visits during the 24 to 30-month follow-up period. We have extensive experience retaining medically vulnerable patients, consistently reporting retention rates in the 90% range. We are thus confident that we will have adequate follow-up data to conduct our outcome analyses.

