## **STATISTICAL ANALYSIS PLAN**

## Statistical Analysis Plan

Baseline variables were summarized by the intervention arm as means and SDs for continuous variables and as counts and percentages for categorical variables. We used a 2-stage modeling strategy to answer our primary hypothesis. All analyses were intent-to-treat. For the first stage, we estimated the intervention effect on weight using a constrained longitudinal linear mixed effects model, using all available data from between 18 months pre-enrollment through 30.5 months postenrollment. We explored nonlinearities for the fixed effects of time and random effects of time in the models, guided by the Bayesian Information Criterion and likelihood ratio tests. The model included fixed effects for time and interactions between time segments and intervention, with a random intercept and random slopes for time. The covariance between random effects was modeled using an unstructured covariance matrix. Randomization was stratified by CHC; thus, we adjusted for CHC in the analyses but did not adjust for other variables. Using this linear mixed effects model, we estimated mean weight change by intervention arm, and the difference between intervention arms in mean weight change, at 6, 12, 18, and 24 months.

Second, we compared the percentage of  $\leq 3\%$  weight gain, our primary outcome, in each arm at 24- months postrandomization using individual empirical best linear unbiased predictors (EBLUPs) from the mixed model. To ensure good predictions, we only used individual EBLUPs from participants with at least 1 EHR weight documented within a 6-month window centered on the 24-month time point (ie, between 21 and 27 months postenrollment). We compared the percentage of  $\leq 3\%$  weight gain in intervention and usual care arms using both a log-binomial model and linear risk model on the EBLUP output, in order to obtain both risk ratios and risk differences, which provide estimates of relative and absolute efficacy, respectively. The extra variability induced by the EBLUPs being predicted from the model was taken into account using a resampling procedure, explained further in the Multimedia Appendices 1 and 2. Sensitivity to the 21- to 27-month window was assessed by obtaining predictions after expanding the window. We additionally used EBLUPs to compare the percentage of  $\leq 3\%$  weight gain in each arm at 6-, 12-, and 18-months postrandomization.

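### The stated power of more than 80% belongs to a time-to-event comparison the SAP does not make; the power of the 24-month primary comparison is not established

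*Combined protocol and SAP*

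**What the plan says.** **Sizing.** In the protocol, Section 2 (Sample size), "The sample size calculation is based on the primary aim examining differences in the time to gain" 3% or more of baseline weight. For follow-up, "we assume a 5% sample loss for each group per month of the study". With 192 per group, the plan "allows us to test the difference between the two distributions with greater than 80% power". A further 15% with no data after baseline brings this to 221 per group (442 in total, up to 455). Alpha, sidedness, effect size and event rate are not given.

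**Primary outcome.** Section 1 first defines it as a change of no more than 3% over 24 months, then states: "Our primary outcome is weight gain prevention at 24 months".

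**Analysis.** The SAP fits a longitudinal mixed model and then compares the percentage with no more than 3% gain, "our primary outcome, in each arm at 24- months postrandomization using individual empirical best linear unbiased predictors (EBLUPs) from the mixed model". On who counts: "we only used individual EBLUPs from participants with at least 1 EHR weight documented within a 6-month window" centred on month 24. The arms are compared "using both a log-binomial model and linear risk model on the EBLUP output". Sensitivity to the window is checked by widening it. No survival analysis and no power statement appear.

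**Expected follow-up.** Section 1 (Follow-up Data Collection) bases its confidence on past trials "consistently reporting retention rates in the 90% range".

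**The concern.** The only power statement in the documents concerns an analysis that the SAP does not list. Three differences keep the figure from carrying over.

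- **Endpoint.** A participant who crosses 3% at month 5 and is back below it at month 24 is an event in one analysis and a success in the other.
- **Information used.** A time-to-event comparison uses everyone's follow-up until loss. The SAP percentage leaves out anyone without a weight at 21 to 27 months, although their earlier weights still inform the mixed model.
- **Effect of loss.** Loss of 5% a month costs a time-to-event analysis some events. If it means no weight in the window, it removes most of the sample from a 24-month percentage.

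At stake is how the result is read. If the confidence interval includes no effect, the reader needs to know what 24-month difference the trial was sized to detect, and the plan does not say.

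**Working it through.** **1. The plan's own figures.** The last step reproduces as 192 × 1.15 = 220.8, or 221. (Dividing instead, 192 / 0.85 = 226 per group; a separate and minor matter.) The power of more than 80% cannot be reproduced, because the inputs needed are not stated. It can only be solved backwards.

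**2. Assumptions.** Log-rank test, two-sided 5% alpha, exponential event times, exponential loss at 5% a month, 24 months of follow-up, 192 per arm. Control incidence of a gain of 3% or more by 24 months: p0 = 30% to 70%. Only the loss rate, the duration and the 192 come from the plan.

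**3. Effect giving exactly 80% log-rank power.**
- Expected events per arm = 192 × λ/(λ+δ) × [1 − exp(−24(λ+δ))], with δ = −ln 0.95 = 0.0513 per month.
- Power = Φ(√(events/4) × |ln HR| − 1.96).
- At p0 = 50%, λ = −ln(0.5)/24 = 0.0289. HR = 0.565 gives 59.1 + 37.2 = 96.3 events and Φ(4.906 × 0.571 − 1.96) = Φ(0.84) = 0.80.
- Intervention incidence p1 = 1 − 0.5^0.565 = 0.324, a difference of 17.6 points.
- Over p0 = 30–70%: HR 0.46–0.63, difference 15–18 points.

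**4. How many would be evaluable.**
- If loss means no weight in the window: 0.95^21 = 0.341 and 0.95^24 = 0.292. That leaves 192 × 0.341 = 65 or 192 × 0.292 = 56 per arm.
- Starting from enrolment: 442 × 0.85 / 2 = 188 and 455 × 0.85 / 2 = 193 per arm, leaving 55–66.
- If 90% are evaluable: 0.90 × 192 = 173 per arm.

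**5. Power of the 24-month comparison of percentages at the same effect.**
- Power = Φ((d − 1.96·se0)/se1), where se0 uses the pooled proportion and se1 the separate ones.
- At p0 = 50%, n = 56: (0.176 − 1.96 × 0.0930)/0.0915 = −0.07, power 0.47.
- At p0 = 50%, n = 173: (0.176 − 1.96 × 0.0529)/0.0521 = 1.39, power 0.92.

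| Evaluable per arm | Power over p0 = 30–70% | Difference needed for 80% power |
|---|---|---|
| 56 | 44–48% | 21–26 points |
| 65 | 50–54% | 20–24 points |
| 173 | 89–92% | 13–15 points |
| 192 | 92–94% | 12–14 points |

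**6. Checks.** If the effect gave 90% log-rank power, the binary power at 56–65 per arm would be about 56–66%. At the 80% log-rank effect, 80% binary power needs about 120–132 evaluable per arm, which is 63–69% of 192 or 54–60% of 221.

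**7. What this leaves out.** It treats the model-predicted status as observed yes/no data, so neither the precision of the predictions nor the resampling variance is included. It also ignores patients who return within the window, and equates ever gaining 3% with status at month 24.

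**The case against.** The strongest reply concerns the size, not the mismatch. The low-power case needs the 5% monthly loss to mean permanent absence from the record. The plan does not say so, and the figure was an input to a time-to-event calculation. Clinic weights are taken at all visits, including acute ones, so one visit in six months makes a participant evaluable, and 54–60% of 221 would be enough for 80% power. The past retention figure may measure something else, so the two figures are unreconciled rather than contradictory. The outcome wording in Section 1 is also looser than the SAP's: a limit held over 24 months could be read as time to gain. All of this stands, and it is why the power figures are illustrative. It does not touch the conflict between Section 2 and the SAP.

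The SAP's widened-window analysis shows that dependence on the window was considered, but it supplies no power for the primary comparison.

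A second reply is that the SAP is written in the past tense, so power stated now cannot change the sample size, and confidence intervals will show the precision achieved. That is true, and it limits the value of the fix. But the documents still state a power that does not belong to the primary analysis. Correcting this from planning inputs is not a post hoc power calculation.

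**Conclusion.** The concern holds, and should be fixed. The mismatch is read directly from the text and needs no assumption: Section 2 powers a time-to-event comparison, and the SAP tests a 24-month percentage in a restricted set.

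The size of the discrepancy is uncertain. Under the assumptions above, the plan's two follow-up figures put power anywhere from about 44% to 92% for an effect with exactly 80% log-rank power. The main driver is the unstated share with a weight at 21 to 27 months. Confidence is high in the mismatch and lower in any single power figure. The trial may be adequately powered or not; the plan does not let the reader tell.

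**What to change.** - In Section 2, keep the time-to-event calculation as the historical basis for the sample size, and state that its power does not apply to the SAP's primary comparison. If its alpha, sidedness, effect size and event rate are on record, add them.
- In the SAP, give the power or detectable difference for the percentage with no more than 3% gain at 24 months, at 442–455 randomised. State alpha, the control proportion, the target difference and the expected share with a weight in the window. Use planning inputs, not observed results; where none is on record, say so and show a range.
- Define the 5% monthly loss, and reconcile it with the retention figure in Section 1.

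The cost is a few sentences and a short calculation. No patients are added and no analysis changes. The only downside is that the stated power may become less favourable.

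### The 15% loss allowance multiplies by 1.15 instead of dividing by 0.85, so 221 per group leaves about 188, short of the 192 behind the power claim

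*Combined protocol and SAP*

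**What the plan says.** All the figures are in the sample size paragraph of the protocol, section 2 (Subject Selection).

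- **Endpoint used for sizing:** "The sample size calculation is based on the primary aim examining differences in the time to gain" at least 3% of baseline weight, compared between the two arms.
- **First loss assumption:** "we assume a 5% sample loss for each group per month of the study". It is stated before the 192.
- **Evaluable sample and power:** "A sample of N=192 per group (Total N=384) allows us to test the difference between the two distributions with greater than 80% power".
- **Second loss assumption:** "Factoring in an additional expected sample loss of 15% (those with no clinical data past baseline").
- **Result:** this "gives a final sample size of N=221 per group (Total N=442, with the possibility of enrolling up to 455").

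The same paragraph opens with the ceiling: "We will recruit up to 455 adult men and women, who speak either English or Spanish". The plan does not state the inflation formula, the exact power at 192, the alpha level, the effect size, or the reason for 455.

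**The concern.** The 15% describes people who are enrolled and then contribute nothing after baseline, so it is a fraction of the enrolled number. To finish with 192 after losing 15% of those enrolled, one divides by 0.85. The stated 221 appears to come from adding 15% of 192 to 192, which always gives too small a number because the loss is then taken from the larger base.

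If so, a trial that stops at its stated final size and loses exactly the share it planned for will miss the evaluable number on which its power claim rests. Readers use the final N to judge whether the trial was adequately sized, so it should agree with the plan's own assumptions.

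**Working it through.** **Inputs, all from the sample size paragraph:** evaluable n = 192 per group (384 total); additional loss d = 0.15; stated final size 221 per group (442 total); ceiling 455 total.

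**1. Reproducing the plan's figure.** Using n × (1 + d):
- 192 × 1.15 = 220.8, rounded up to 221 per group
- 384 × 1.15 = 441.6, rounded up to 442 in total

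Both stated figures are reproduced.

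**2. The inflation that matches the stated loss.** Using n / (1 − d):
- 192 / 0.85 = 225.9, rounded up to 226 per group
- 2 × 226 = 452 in total
- Check: 226 × 0.85 = 192.1

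This is 5 per group and 10 in total more than stated (5 / 221 = 2.3%).

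**3. What each enrolment total leaves after a 15% loss.**

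| Enrolled, total | Evaluable, total | Evaluable per group |
|---|---|---|
| 442 | 375.7 | 187.85 |
| 452 | 384.2 | 192.1 |
| 455 | 386.75 | 193.4 |

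The requirement is 384 in total, 192 per group. The stated 442 falls about 8 short in total, 4 per group. The loss that 221 can absorb is 1 − 192 / 221 = 13.1%, not 15%.

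**4. Effect on power.** The exact power at 192 is not given, so I take a range. I assume two-sided alpha 0.05, the same effect, and information proportional to sample size. With p0 the power at 192, power at n is Φ[(1.960 + z(p0)) × √(n / 192) − 1.960].

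| Power at 192 (assumed) | Power at 187.85 | Power at 193.4 (455 enrolled) |
|---|---|---|
| 80% | 79.1% | 80.3% |
| 81% | 80.2% | 81.3% |
| 82% | 81.2% | 82.3% |
| 85% | 84.2% | 85.3% |
| 90% | 89.4% | 90.2% |

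Power at 187.85 stays at or above 80% if power at 192 is at least about 80.9%.

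The 192 itself cannot be re-derived, because alpha, effect size and event rates are not stated. The point does not depend on how 192 was obtained.

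**The case against.** The arithmetic is hard to contest. The case on the other side is that it hardly matters.

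- **The power claim has slack.** The plan says "with greater than 80% power", not exactly 80%, and does not call 192 a minimum. A fall below 80% therefore cannot be demonstrated. This stands, but the slack cannot be confirmed either, because the exact power is not given.
- **The ceiling covers it.** Enrolling 455 would leave 386.75 evaluable, above 384. This stands if the ceiling is reached. But 442 is named as the final size and 455 only as a possibility, with no link to the loss allowance, so stopping at 442 complies with the plan and still misses 192.
- **The 15% is only a forecast.** The follow-up part of section 1 reports retention in the 90% range in earlier work. At a 10% loss, 221 leaves 221 × 0.90 = 198.9. That retention figure may not measure the same thing as having a record after baseline, and the sample size paragraph adopts 15%. A calculation should agree with its own assumption.
- **The monthly loss might absorb the gap.** It does not: the 15% is described as additional to it.
- **The SAP analyses something else.** It compares the percentage with at most 3% gain at 24 months, among participants with a recorded weight between 21 and 27 months, whereas 192 was derived for a time-to-event comparison. Correcting 221 to 226 therefore does not establish power for that analysis. This is a fair limit on what the correction achieves, but it does not make 221 right.
- **It may be too late.** The SAP is written in the past tense and the protocol gives funding as having continued to April 30, 2023. If enrolment has closed, only a restatement is useful.

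**Conclusion.** The concern holds. The stated final size of 221 per group is the evaluable number multiplied by 1.15, and under the plan's own 15% loss it yields about 188 per group instead of 192. This follows from the stated figures alone, given that the loss is a share of those enrolled.

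The consequence is small. The shortfall is about 2% of the evaluable sample and costs at most about 0.9 percentage points of power across the range examined, under the assumptions listed with the power calculation. Whether power drops below 80% cannot be settled from the documents. This is a sizing statement that needs correcting; it does not threaten the validity of the trial.

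**What to change.** Change one sentence in the sample size paragraph, in one of two ways:

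1. State the enrolment target as 226 per group (452 total), calculated as 192 / (1 − 0.15).
2. Keep 442 and state that, after the 15% loss, about 188 per group (376 in total) are expected to be evaluable, with the power for that number computed from the original design inputs.

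If enrolment has closed, the second form is the useful one, applied as a correction to the sample size justification. In either case, give the inflation formula and the exact power at 192 so that the figure can be checked.

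The cost is a sentence of text. The first option adds 10 participants to the stated target but stays within the ceiling of 455.
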